2.1. Rationale

The Center for Malariaology, Parasitology, and Entomology (CMPE) in Lao PDR over the past two years has completed the National Strategic Plan 2016-2020¹², and new National Surveillance Guidelines that includes case-based surveillance and focal response including RACD. After some setbacks from 2011-2015, there has been major progress and incidence has recently fallen dramatically in several southern provinces, making foci-based active surveillance strategies now feasible in these areas.

Under the current national and regional artemisinin initiative 2 elimination (RAI2E) funding, VMWs and Malaria Posts will be expanded to improve coverage across these provinces. Household-level RACD has yet to be operationalized in southern Lao PDR, but is planned for roll-out over the next year by teams from national, provincial, and district levels. In order to maximize sustainability and impact, this strategy will need to be community-based and target the highest risk populations.

The current management of *P. vivax* cases and G6PD deficiency varies by country; in Laos, current policy states that all *P. vivax* cases are to be tested for G6PD deficiency and only those without deficiency receive a 14-day course of primaquine. Rigorous follow-up of cases to monitor safety and adherence is not conducted, and the use of G6PD testing and primaquine treatment has not yet been widely operationalized.

The research proposed here will evaluate the effectiveness and feasibility of a community-based reactive case detection strategy when combined with the use of HS-RDTs, targeting high-risk villages and forest populations, and *P. vivax* testing treatment adherence after referral to district or provincial-level facilities. Results of this research will have direct implications for continued roll out and sustainability of community-based foci management, and provide practical guidance that other malaria programs can utilize.

2.2. Significance

We propose to conduct this operational research in a large number of the remaining active foci across in two of the remaining higher burden provinces in southern Lao PDR. The findings will help Laos assess the benefit and potential challenges of community-based approaches to active foci management including RACD for *P. falciparum* and *P. vivax*, and the effectiveness of RACD using HS-RDTs in this context, which will provide a rigorous evidence base for other countries in the GMS applying these approaches. Importantly, this trial will incorporate community-based approaches for targeting high-risk forest workers, which are a uniquely prevalent high-risk population in the GMS.

2.3. Primary aim

The primary aim of this project is to determine the effectiveness and feasibility of enhanced community-based reactive case detection (RACD) in Lao PDR, targeting high-risk villages and forest workers, for reducing *P. falciparum* and *P. vivax* transmission.

2.4. Primary research questions and hypotheses

This project aims to answer the following research question and hypotheses:

*Is community-based RACD using HS-RDTs targeting both village and forest working populations more effective than the standard of care (community case management, and RACD conducted by district surveillance teams) in reducing *P. falciparum* and *P. vivax* confirmed case incidence and parasite prevalence over an 18-month intervention period?*

Null hypothesis 1: Compared to standard of care, which includes case management and RACD with conventional RDTs and is directed at villagers, there is no additional benefit of enhanced community-based RACD, which is conducted by VMWs, uses HS-RDTs, and targets forest workers in addition to villagers, for reducing *P. falciparum* and *P. vivax* confirmed case incidence and parasite prevalence over an 18-month period in Lao PDR.

Research hypothesis 1: Enhanced community-based RACD will be more effective than standard of care case management and RACD at reducing *P. falciparum* and *P. vivax* confirmed case incidence and parasite prevalence over an 18-month period in Lao PDR.

2.5. Study overview

To test this hypothesis, this study will employ a cluster randomized controlled trial design with two comparison arms:

1. **Control:** standard of care - passive case management provided through community-based VMWs and existing health facilities; includes village-based RACD with conventional RDTs conducted by district surveillance teams.
2. **Enhanced community-based RACD:** RACD conducted by community-based VMWs using both HS-RDTs and conventional RDTs within villages and among forest workers.

The primary outcome measures to assess effectiveness include *P. falciparum* and *P. vivax* confirmed case incidence over the study period; PCR-based *P. falciparum* and *P. vivax* prevalence at endline; and HS-RDT test positivity rate in village and forest worker RACD. Secondary outcomes measures will examine the operational feasibility, safety, and acceptability of VMW-led reactive approaches and G6PD testing, referral to district or provincial-level facilities, safety and treatment adherence for *P. vivax* cases. The trial will be implemented between June 2019 and December 2020 in Lao PDR. The primary evaluation will be conducted following an end-line cross-sectional survey in November/December 2020.

2.6. Summary of ethical issues

Prior to implementation, the protocol and all related project activities will be reviewed and approved by the institutional review boards in Lao PDR and at UCSF. For other partnering institutions (i.e., University of Texas Southwestern, University of Massachusetts, Tulane University), requests will be made for reliance on UCSF IRB. The protocol will be submitted to CDC Human Subjects for non-engaged review. Participation in either the research or intervention is voluntary. Individuals will be included in the study only if they or their parents/guardians provide written informed consent. The consent process will be conducted in appropriate local languages at the start of every new contact with an individual. For individuals under 18 years of age, informed consent will be obtained from a parent or guardian. Oral assent for adolescents 12 to <18 years of age will be obtained in addition to consent from a parent or guardian. As part of the informed consent, specific consent for the pregnancy test will also be required for female participants of child-bearing age.

The safety risks associated with participation in this trial are expected to be minimal. The study drugs, which are first-line treatment regimens for the respective areas in Lao PDR, artemether-lumefantrine (AL) and PQ in G6PD non-deficient individuals, are well tolerated and safe. Prior to drug administration, participants will be asked about known contraindications, and if such contraindications are reported, participants will be restricted from taking the relevant medication. PQ administered as a single low dose has been found to be safe in individuals with any of the G6PD variants and is recommended by WHO without G6PD testing¹³. The 14-day course of PQ will only be given to G6PD non-deficient individuals after G6PD testing with a qualitative RDT. Should a subject be misclassified as G6PD non-deficient when in actual fact they are G6PD deficient and had begun their 14-day PQ regimen, participants will be asked to stop treatment with primaquine immediately and a

robust follow-up and severe adverse event management system will pick up early cases of hemolysis, stop treatment with primaquine and if necessary refer for further clinical management.

The risks associated with loss of privacy in this study are likely to be low. To ensure confidentiality is maintained, all information will be treated as private by study personnel, and records kept securely in locked filing cabinets and offices. Electronic records will be kept on a secure, firewall- and password-protected server. For all data collected as part of the study, participants will be assigned a unique identification number. No personal identification information such as names will be used in any reports arising out of this research. All project staff will be trained on procedures for maintaining confidentiality.

Study participants with malaria infections identified by RDTs/HS RDTs will benefit directly from treatment with recommended first line treatment.

Participants will not be paid to take part in this study. Most assessments will be conducted at households or working sites, which will eliminate the need for participant travel and minimize opportunity costs for the participants. Any diagnosis and treatment associated with the study will be provided free of charge.

3 Methodology

3.1. Study sites

The selected study sites include health facility catchment areas in two of the highest burden provinces in Southern Laos. All selected health facilities had at least 3 malaria cases in the previous year. The districts included in Laos are shown in Table 1 and Figure 1. In addition to the number of health facilities included in the study, the total number of villages and population in those selected areas, and the *P. falciparum* and *P. vivax* annual parasite index (API) for Oct 2017 – Sep 2018 is shown. The anticipated period for the study is June 2019 – December 2020.

Table 1. Overview of incidence and population within selected health facility catchment areas in Lao PDR

District	Province	Total health facilities	Total villages	Total population	Pf 2017-18 (API)	Pv 2017-18 (API)	Total cases 2017-18 (API)
Khong	Champasak	4	32	22764	3.43	2.81	6.24
Mounlapamok	Champasak	4	23	18005	0.56	1.94	2.5
Pathoumphon	Champasak	3	34	22975	3	4.61	7.62
Sukhuma	Champasak	1	8	10300	0.58	1.65	2.23
Samouay	Saravan	3	28	6177	0.65	13.11	13.76
Saravan	Saravan	3	35	17877	1.51	1.29	2.8
Taoi	Saravan	5	57	12713	16.6	1.65	18.25
Toumlan	Saravan	6	46	18366	6.81	1.47	8.28
Vapy	Saravan	3	37	18621	3.11	2.09	5.21
Total		32	300	147,798	3.98	2.79	6.77

Figure 1. Selected study districts in Lao PDR (highlighted in orange)

3.2. Study population

The study population includes all villagers and forest workers in the selected health facility catchments. Inclusion and exclusion criteria for the interventions are described below.

Inclusion and exclusion criteria

Inclusion criteria

Subjects must fulfill the following inclusion criteria to be eligible for enhanced RACD:

- **Index cases:**
 - Presented as a confirmed malaria case to an intervention health facility or village malaria worker, and lives in a village within a selected intervention health facility catchment area, or worked or spent at least one night at a forest or forest-fringe site in the past 30 days located within an intervention health facility catchment area
- **Village residents:**
 - Lives in a village within a selected intervention health facility catchment area and in one of the five households closest to the residence of an index case of malaria
- **Co-worker/traveler referral:**
 - Worked or traveled and spent at least one night in forest in past 30 days in same location within an intervention health facility catchment area as an index case of malaria
- **All participants:**
 - Willing and available to participate in the study
- Informed consent for participant under the age of 18 will be provided by the parent or guardian.

Exclusion criteria:

- **All RACD referrals:**
 - Previous participation in the study as a result of any RACD event in the past 30 days.

- Individuals with severe disease or drug contra-indications will be excluded from the treatment component only (detailed below)

3.3. Interventions

Each intervention cluster (i.e., health facility catchment area) will be randomly assigned to either the RACD intervention or control arm (in a 1:1 ratio) before the study begins. The randomization process is described in more detail in section 3.4.2.2 below. Interventions (RACD) will be conducted by VMWs and/or community volunteers in response to an index case (presenting to VMW, malaria post, health facility, or other testing facilities) occurring anywhere within a selected intervention health facility catchment area. At presentation, all index cases will initially be asked about recent forest exposure. The intervention response for cases with no history of forest exposure in the past two months will be conducted only at the village level, while the response for cases with history of recent forest exposure will include both village and forest-worker populations. Forest-worker RACD will be conducted at recent work sites if accessible and located within the health facility catchment and/or amongst peer forest-goers referred by the index case. VMWs in intervention villages will maintain a register of forest workers and locations to assist them with tracking. In Lao PDR, health center staff will assist with RACD during the first six months of the study only, after which point VMWs will operate independently.

Index case capture

Interventions will be initiated after an individual from a cluster assigned to an intervention is diagnosed with malaria and notified to the study team. Suspected malaria cases attending local health services (hospital, health center, health post, or VMW) will be tested with an RDT or microscopy according to routine practice. All cases parasitologically confirmed by RDT will be treated according to national guidelines and asked for informed consent to participate in the study. If the patient gives informed consent, the VMW or health staff will promptly notify the study team using mobile phone. A short screening questionnaire will be administered to determine location of residence and recent forest or other travel. Additionally, finger prick blood will be collected on DBS from the index case for subsequent analyses.

3.3.1. Reactive case detection (RACD)

Household RACD

Within 7 days of the index case notification, the VMW will conduct the investigation visit at the residence of the index, and the index case will be interviewed using a standard case investigation form. All members of the index case's household will then be invited to participate in the study. A GPS point will be captured for the index house, and the nearest five households around the index case's household will be identified by the VMW. In the neighboring five households, a GPS point will be captured and all household members, including temporary visitors, will be invited to participate in the study. Household members and parents/guardians of children will be verbally informed of the general purpose of the intervention and the study, and the possible risks and potential benefits associated with participation. Individual written consent will be obtained at each household and for each blood sample collected for testing. For children <6 to 12 years old, consent will be obtained from the parent or guardian. For children 12 to <18 years of age, the child's oral assent will also be required in addition to parents/guardians' consent. All informed consent procedures will be conducted in the appropriate local language. All consenting participants will be interviewed using the participants' questionnaire to assess history of malaria in previous year, travel information, and utilization of malaria prevention measures.

A finger stick blood sample will be collected for each consenting individual for testing with the HS-RDT for *P. falciparum*, a standard combination RDT, and four blood spots on filter paper. Individuals will be told of their test result and a positive test result on either RDT will prompt treatment as per the national treatment guidelines. See tables 2 and 3 below for treatment guidelines.

In the event that household members are not present at the time of testing, the VMW will ask if any absent household member has been ill with fever during the previous two weeks. If any absent household members are reported as having recent fever history or if any other household members test positive for malaria, the VMW will schedule a time to revisit the household. At this time, the VMW will administer the informed consent form to any previously absent household members and then test these individuals (and treat positive cases). Febrile individuals testing negative by RDT(s) will be referred to the nearest health center.

RACD of cases' co-workers/co-travelers

Index cases will be screened by the VMW at their households at the time of case investigation to determine if they have traveled or worked in a forest or forest-fringe area within the past 30 days. If eligible, the case will trigger two reactive recruitment strategies to screen and treat others who recently traveled or worked with the case in a forest or forest-fringe location:

1. *Peer-referral RACD (PR-RACD)*: In this strategy, the case will identify specific co-travelers or co-workers resident in their village who had spent the night with the case at a forest or forest-fringe area and spent the night there in the past 30 days.
2. *Venue-based RACD (VB-RACD)*: In this strategy, co-workers will be recruited directly from (accessible) forest or forest-fringe work sites where the index case worked and spent at least one night in the past 30 days.

Participating index cases who meet eligibility criteria will be asked to provide a list of all people who have worked or traveled in the forest or forest-fringe with him/her in the past 30 days between dusk and dawn and their contact information (names, phone numbers, home addresses) (peer-referrals). The questionnaire will elicit from index case all forest and forest-fringe work sites where the case has spent the night in the past 30 days, as well as contact information for any respective employers.

For PR-RACD, VMWs will contact peer-referrals by phone, at their home, or through village leaders and invite them to participate in a survey interview and malaria testing at a time and place that is most convenient. This may be the referral's place of residence, a health facility, or another location in the village that provides sufficient confidentiality, such as a coffee shop.

- a. Peer referrals will be screened for eligibility by the VMW and, if eligible, informed consent will be conducted in the appropriate local language.
- b. Consenting referrals will provide a fingerstick blood sample for testing with the HS-RDT, standard combination RDT and four blood spots on filter paper. If infection is present according to any RDT, they will receive treatment following the guidelines in the following section.
- c. All consenting referrals will complete an interviewer-administered survey questionnaire.

For VB-RACD, if available, employers will be contacted by the VMW to coordinate a potential visit to identified work sites.

- a. Work sites considered for VB-RACD will meet the following criteria:
 - Case reports that the work site is currently active
 - Case reports there are at least five other workers who work or sleep there (the minimum threshold ensures that screening there is worthwhile, given logistic constraints, and will be specified in SOP)
 - The work site is safe to visit and accessible
 - The nearest VMW has necessary permissions to travel to site

- b. The nearest VMW will travel to any such work sites identified
- c. All workers present at the site(s) will be screened for eligibility and, if eligible, informed consent will be conducted.
- d. Consenting referrals will provide a finger stick blood sample for testing with the HS-RDT, standard combination RDT, and four blood spots on filter paper. If infection is present according to any RDT they will receive treatment following the guidelines in the following section.
- e. All consenting referrals will complete an interviewer-administered survey questionnaire.

All participants will receive a small token of participation such as a bar of soap or phone credit.

Forest workers may be difficult to reach at their places of residence as they are often away from the household. When following-up with PR-RACD referrals, VMWs will attempt to contact them directly by phone multiple times and visit the household if the address was provided or they are familiar with the location. When referrals are unreachable by phone or the residential location is unknown, VMWs will elicit the help of the village leader to identify where they live or how best to contact them. VMWs will record each contact into a register of all individuals in their community known to travel to forest, the location of their residence, and location of work-site if possible.

Case Management and Follow-up

All individuals who test positive by either HS-RDT or Standard RDT will be told of their results and treated on site per national guidelines:

- Individuals with *P. falciparum* infection will be treated with an age-appropriate course of artemether-lumefantrine (AL) and a single low dose of primaquine (SLD-PQ). Weight-based dosing is described in Tables 2 and 3 below.
- At all study sites in Lao PDR, patients with a *P. vivax* infection identified by RDT (both febrile and asymptomatic) will be given a unique coded and signed informational letter directing them to the nearest district hospital (or other testing facility) for G6PD deficiency testing and possible radical cure administration depending on results. Study contact information will also be included if the participants present at other health facilities. At the health facility, G6PD normal individuals will be treated with AL and a 14-day course of PQ, whereas G6PD deficient individuals will receive AL alone as per the national guidelines and referred to a hospital for further primaquine management decisions. The study staff will meet with district hospital and health facility staff monthly from all study areas and nearby district hospitals and health facilities to collect these forms, with small incentives for health staff to report receiving a study card (phone top up card, etc.) to maximize data completeness. After six months of implementation, a subset of VMWs will begin conducting qualitative G6PD testing and treatment administration at the community-level with the assistance of a health facility staff member.

Table 2. AL weight-based dosing

Body weight (kg)	Tablet strength (mg)		Tablets/dose	Mg of drug per dose		Tablets/day
	Artemether	Lumefantrine		Artemether	Lumefantrine	
5 to 14	20	120	1	20	120	1 tablet given twice* per day for 3 consecutive days

15 to 24	20	120	2	40	240	2 tablets given twice* per day for 3 consecutive days
25 to 34	20	120	3	60	360	3 tablets given twice* per day for 3 consecutive days
35 or greater	20	120	4	80	480	4 tablets given twice* per day for 3 consecutive days
*Approx. 8 hours between doses 1 and 2. Approx. 12 hours between all other consecutive doses.						

Table 3. Weight-based dosing of SLD- Primaquine (.25 mg/kg) for *P. falciparum*

Body weight (kg)	SLD-PQ dose (7.5 mg tablet) (as base)	Tablets
10 to < 25	3.75	1/2
25 to < 50	7.5	1
50 to 100	15	2
*Given as SLD in addition to AL for P falciparum positive		

Table 4. Age-based dosing of Primaquine for *P. vivax*

Items	Dose	No. of tablet/day	Frequency	Duration
G6PD Normal				
Children				
4-8 years old	5 mg/day	1/3	Once per day after meal	14 days
9-14 years old	10 mg/ day	2/3		
>14 years old (adults)	15 mg/ day	1		

Per national guidelines in Laos, AL will not be given to women who are pregnant or may be in their first trimester. All women of reproductive age with a last menstrual period greater than four weeks positive HS RDT or Standard RDT will be offered a pregnancy test. Pregnancy testing and consent will be embedded in the participant questionnaire. Any woman who acknowledges pregnancy in the first trimester or confirmed by a positive pregnancy test or refuses to take a pregnancy test will be excluded from receiving AL and will be referred to the nearest health facilities for treatment.

Contraindications to primaquine include pregnancy (any trimester), age less than 12 months, infants weighing less than 10 kilograms, women in the first 12 months of breastfeeding, and prior allergic reaction to primaquine. Participants with contraindications to primaquine will not be excluded from the study and will receive first-line treatment alone, provided they are eligible.

All individuals with suspected severe malaria or other severe illness (including those with symptoms of severe anemia, prostration, impaired consciousness, respiratory distress, convulsions, circulatory collapse, abnormal bleeding, jaundice or passing dark urine) will be referred to the nearest health facility for clinical assessment and treatment.

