3.4.2.3. Primary outcome measures

1. Confirmed *P. falciparum* and *P. vivax* malaria parasite incidence: defined as the number of OPD malaria confirmed and suspected cases per person per year for each HCCA, as ascertained from the health facility registers, utilizing administrative catchment population size estimates for the exposure denominator.
2. PCR-based *P. falciparum* and *P. vivax* parasite prevalence in sampled HCCAs: defined as the proportion of individuals ≥ 18 months old with *P. falciparum* or *P. vivax* infection (detected by PCR) out of all individuals ≥ 18 months tested within the endline survey (2020).
3. HS-RDT/RDT -based test positivity rate in village and forest-based reactive case detection: defined as the proportion of all individuals tested by HS-RDT/RDT in response to an index cases, with a positive HS-RDT/RDT, among the population older than 18 months.

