The HS-RDT and RDT test positivity rate will be estimated for the RACD areas during each intervention. This will be done as soon as data on HS-RDT results are available. Differences in test positivity measures over time and between village and forest base samples will be assessed using a χ^2 test, as well as logistic regression models to account for potential confounding factors.

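### Household RACD tests absent contacts only after a reported fever or a positive result, and pooling those tests makes outcome 3 positivity partly a product of the revisit rule

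*Protocol*

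**What the plan says.** Under Household RACD, Section 3.3.1 of the protocol invites all members of the index household and the five nearest households. When some are away, the worker asks whether an absent member has been feverish in the previous two weeks. A return visit is arranged on this condition: "If any absent household members are reported as having recent fever history or if any other household members test positive for malaria". At that visit "the VMW will administer the informed consent form to any previously absent household members and then test these individuals". No return is specified for a household with neither trigger.

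Section 3.4.2.3, item 3, gives the primary outcome as "defined as the proportion of all individuals tested by HS-RDT/RDT in response to an index cases, with a positive HS-RDT/RDT", among people older than 18 months. It does not separate first-visit tests from revisit tests.

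Under Outcome 3, Section 3.4.2.6 states: "The HS-RDT and RDT test positivity rate will be estimated for the RACD areas during each intervention". It adds: "Differences in test positivity measures over time and between village and forest base samples will be assessed", by a chi-square test, "as well as logistic regression models to account for potential confounding factors".

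Forest recruitment, also in Section 3.3.1, works differently. Peer referrals are pursued by repeated calls, home visits and village leaders, whatever their symptoms or anyone's result. Worksite screening covers every worker present. The endline survey (Section 3.4.2.5.2) allows up to four household visits, also without a fever or result condition.

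**The concern.** One of the two triggers is the outcome itself, a positive test in the same household. The other, fever, is associated with infection. Absent people who enter the numerator and denominator through a revisit are therefore more likely to be positive than absent people who are not revisited.

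How far this moves the rate depends on how many members are away and how often fever is reported. Both can change with season and place. A trend in village positivity, or a gap between village and forest positivity, could then partly reflect the revisit rule. The planned regression adjusts for confounders, and Section 3.4.2.5.3 mentions clustering by index case. Neither deals with how a person came to be tested.

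**Working it through.** **The plan's own figure.** Section 3.4.2.4.3 expects 720 cases, 5 households per case, 4 people per household and 4 forest workers per case. Village: 720 × 5 × 4 = 14,400. Forest: 720 × 4 = 2,880. Total: 17,280, as stated. The village figure counts all four people in every household, so it makes no allowance for absent members who are never revisited. The section gives no formal sample size for this outcome.

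**Inputs.** Household size 4 is from the protocol. The rest are assumptions:
- positivity among members present: 0.5%, 1% or 2.5%
- absence: 20% or 40%
- fever: 20% of infected and 3% of uninfected, or 30% and 5%
- household clustering: lognormal frailty (SD 1.0 or 1.5) or beta-binomial (ICC 0.02 or 0.10)
- risk in absent relative to present members, r: 1, 1.5 or 3

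Each scenario simulates 1,000,000 households and applies the protocol's trigger.

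**Formulas.** Someone must be present for a first visit, so with absence a the absent share in visited households is a′ = (a − a⁴)/(1 − a⁴). This is 0.199 at 20% and 0.384 at 40%. Let p be first-visit positivity, s the share of absent members revisited and v positivity among those revisited.

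- All contacts: p × [1 + a′(r − 1)]
- Pooled: [(1 − a′)p + a′sv] / [(1 − a′) + a′s]

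**Example.** p = 1%, frailty SD 1.0, fever 30% and 5%; s and v come from the simulation.

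| Absence | r | s | v | Pooled ÷ first-visit | All ÷ first-visit | Pooled ÷ all | First-visit ÷ all |
|---|---|---|---|---|---|---|---|
| 20% | 1 | 10.3% | 3.5% | 1.06 | 1.00 | 1.06 | 1.00 |
| 40% | 1 | 12.3% | 3.2% | 1.15 | 1.00 | 1.15 | 1.00 |
| 20% | 3 | 11.0% | 10.2% | 1.24 | 1.40 | 0.89 | 0.71 |
| 40% | 3 | 13.1% | 8.7% | 1.58 | 1.77 | 0.90 | 0.57 |

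Row 2 by hand: (0.616 × 1.00 + 0.384 × 0.1226 × 3.15) / (0.616 + 0.384 × 0.1226) = 0.764 / 0.663 = 1.15%.

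**Absence alone.** Rows 1 and 2 have the same infection risk throughout. Raising absence from 20% to 40% moves pooled positivity from about 1.06% to 1.15%, while first-visit positivity stays at 1.00%.

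**Full grid.**

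| r | Pooled ÷ all | First-visit ÷ all |
|---|---|---|
| 1 | 1.05-1.21 | 1.00 (within simulation error) |
| 1.5 | 0.97-1.14 | 0.83-0.92 |
| 3 | 0.80-1.02 | 0.56-0.74 |

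About 6-18% of absent members are revisited. Their positivity is about 3 to 10 times that of absent members left untested.

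**Which trigger matters.** If fever is unrelated to infection (5% in both groups; p = 1%, absence 30%, r = 1), the pooled rate is only 1.01-1.02 times the first-visit rate at ICC 0.02, and 1.07 times at ICC 0.10. The positive-test trigger matters mainly when infections cluster in households.

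**The case against.** The best counter-argument is that the outcome is defined as positivity among those tested, which is the yield of RACD as delivered, and revisits are part of delivery. Population prevalence is outcome 2 and has its own random sample. This stands, and it is why the pooled rate should be kept.

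A reader might infer that first-visit positivity should replace the pooled rate. The documents do not support that. Section 3.3.1 says forest workers are often away from home, and Section 2 links forest-fringe work to higher risk, so absent members may well carry more infection. At r = 1.5 and r = 3, first-visit positivity is further from the all-contact rate than pooled positivity in every scenario of the grid.

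Other strong readings also fail. Only the household stream has a result-dependent rule. An absent member named as a co-worker or co-traveller may still be reached through forest RACD, so untriggered absence does not always mean untested. The village and forest streams differ by design in other ways as well.

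The absolute size is modest. At 1% positivity, 20-40% absence and equal risk, the example's excess is about 0.06-0.15 percentage points. The simple 95% half-width for 14,400 tests is 1.96 × √(0.01 × 0.99 / 14,400) = 0.16 points, before clustering.

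Finally, coverage reporting (Sections 3.4.3.2 and 3.4.3.5) will show how many eligible people were missed, and a visit-type stratum could be added in the SAP. Coverage figures do not separate the tests by visit type, however, and the protocol itself fixes the pooled definition and the comparisons. The RACD questionnaire (Appendix 8.7) is listed but not reproduced, so it may already hold a visit field.

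**Conclusion.** The concern holds for outcome 3 in the RACD areas. The pooled rate is valid as a yield but does not estimate positivity in all eligible contacts. Comparing it over time, or with forest samples, mixes infection with the working of the revisit rule.

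Under the assumed inputs it is about 5-20% too high relative to all contacts at equal risk, and roughly 0-20% too low at three-fold risk. The direction cannot be known from the data, because untriggered absent members are not tested through the household pathway. First-visit positivity is free of the trigger and stable against absence, but it describes only those present, at about 0.55-0.75 of the all-contact rate when absent members carry three times the risk. Neither rate is sufficient alone.

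A reader might infer that the trial's effectiveness conclusion is at risk. It is not: outcome 3 has no between-arm test, and the tests of outcomes 1 and 2 do not use these data. All sizes rest on assumed absence, fever, clustering and relative risk, none of which the protocol supplies.

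**What to change.** - **RACD form:** record whether each test was done at the first visit or a revisit and, for a revisit, which trigger applied. Confirm first whether the form already does this.
- **Section 3.4.2.3, item 3:** keep the pooled rate and label it the yield of RACD as delivered. Report first-visit and triggered-revisit positivity as separate strata, with numbers absent, revisited and left untested.
- **Section 3.4.2.6, Outcome 3:** run the over-time and village-versus-forest comparisons on first-visit tests as well as on the pooled data.
- **Interpretation:** state that first-visit positivity describes only contacts present, and that the pooled rate does not estimate positivity in all eligible contacts.

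The field rule for revisits stays as it is. The cost is one form field and a second set of estimates. No data are discarded. If visit type is not recorded at the time, the two groups may not be separable later.
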